8.3.2.1.1. Evaluation of Dose Response for ACQ-5 and Pre-Bronchodilator FEV₁

A dose response analysis for change from baseline to Week 24 in ACQ-5 score and prebronchodilator FEV_1 will be conducted to evaluate the relationship between increasing dose and the effect of GB001, using the primary analysis method of these secondary efficacy endpoints. Differences in LS means and SEs for all pairwise comparisons will be provided. In addition, Tukey's multiple comparisons test (i.e. Tukey's honest significance difference) will be used to compare all possible pairwise means to test which pairwise means differ while adjusting nominal type 1 error at 5%. The simultaneous 95% CIs and p-values from Tukey's test will be reported. Box plots for mean change from baseline to Week 24 by treatment group will be presented.

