4.3. Justification for Dose

This study will assess the dose-response relationship of 3 doses of GB001 (60 mg, 40 mg, and 20 mg) in adult subjects with moderate to severe asthma.

The GB001 40 mg dose was selected based on the anticipated pharmacokinetics (PK) and exposure levels extrapolated from the results of two Phase 2 studies with GB001 (Study PTR-36-201 and ADC3680-07) and based on prior efficacy and safety results from these studies. In Study PTR-36-201, GB001 20 mg and 5 mg doses were evaluated in an asthma treatment withdrawal design. Both doses of GB001 were effective in decreasing the proportion of subjects with asthma worsening/exacerbations as compared to placebo, with the 20 mg dose producing a larger treatment effect (20 mg: 20.8%; 5 mg: 32.7%; placebo: 52.8%). In addition, only the 20 mg dose demonstrated statistical significance for the endpoints of asthma control (ACQ-5) and time to asthma worsening relative to placebo. No improvements in lung function were observed, while less worsening of lung function was seen in the GB001 groups compared to placebo. A comparable safety profile was observed across all treatment arms (including placebo) in this study. Based on this data, the 40 mg dose has been selected for the current study.

To characterize the dose-response curve, 1 dose level below and 1 dose level above the 40 mg dose are included in the current study. The 20 mg dose has been included as a potentially suboptimal dose based on data generated from a Phase 2 study of GB001 versus placebo (Study ADC3680-07). This study found that GB001 20 mg daily produced some efficacy, as measured by improvements in ACQ scores, but this dose level did not result in improvements in lung function. The 60 mg dose is included to assess whether greater efficacy may be achieved beyond that of the 40 mg dose, since no improvements have been seen in lung function with lower doses to date.

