8.1.3. Multiple Comparisons/Multiplicity

In general, statistical testing of efficacy endpoints will be made without any adjustments for multiplicity, and all statistical hypothesis tests will be two-sided with a significance level of 0.050.

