8.3.1.2. Evaluation of Dose Response for the Primary Endpoint

A dose response analysis will be conducted to evaluate the relationship between increasing dose and the effect of GB001, using the primary analysis method of the primary endpoint.

A one-sided, asymptotic, Cochran-Armitage test for trend (Cochran, 1954; Armitage, 1955) will be used to test if the response proportion with asthma worsening decreases linearly with increasing dose level (placebo, 20 mg, 40 mg, 60 mg). The p-value from the test will be reported.

For this test, the null hypothesis, H0 ($\Pi_0 = \Pi_{20} = \Pi_{40} = \Pi_{60}$) is: There is no linear trend in binomial proportions of response across increasing levels of dosage.

The alternative hypothesis, (H1) ($\Pi_0 \ge \Pi_{20} \ge \Pi_{40} \ge \Pi_{60}$) is: There is a decreasing trend in binomial proportions of response across increasing levels of dosage.

To further evaluate the dose response relationship, the ORs and corresponding 95% CIs for the 3 pairwise comparisons among each of the GB001 treatment groups will be provided (60 mg vs 20 mg, 60 mg vs 40 mg, 40 mg vs 20 mg). Percentage reductions and corresponding 95% CIs will also be provided.

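### The dose-response analysis planned for ACQ-5 and pre-bronchodilator FEV₁ contains no test that uses dose order

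*SAP*

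**What the plan says.** SAP 8.3.2.1.1 introduces a dose-response analysis of change from baseline to Week 24 in ACQ-5 and pre-bronchodilator FEV₁, done "to evaluate the relationship between increasing dose and the effect of GB001, using the primary analysis method of these secondary efficacy endpoints". It lists three outputs:

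- Estimates: "Differences in LS means and SEs for all pairwise comparisons will be provided".
- Tukey's honest significant difference, which "will be used to compare all possible pairwise means to test which pairwise means differ", with type 1 error held at 5% over the set of pairs and simultaneous 95% CIs and p-values reported.
- Box plots by treatment group.

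For the primary endpoint, SAP 8.3.1.2 opens with nearly the same purpose and names "A one-sided, asymptotic, Cochran-Armitage test for trend" across placebo, 20, 40 and 60 mg. It then adds odds ratios for the three dose-against-dose pairs. Protocol 4.3 makes dose response an aim of the trial: "This study will assess the dose-response relationship of 3 doses of GB001". SAP 8.1.3 sets the general rule that efficacy tests are not adjusted for multiplicity and that "all statistical hypothesis tests will be two-sided with a significance level of 0.050".

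**The concern.** A dose-response question concerns ordered groups: does the effect change in a consistent direction as dose goes from 0 to 20, 40 and 60 mg? Tukey's procedure asks a different question, namely which of the six pairs of means differ. Relabelling the arms leaves its overall result unchanged, and a significant pair need not reflect a monotone relationship. The section has no trend contrast, ordered alternative, slope or dose model.

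At stake is what the report can say about two secondary endpoints that the SAP itself singles out for dose-response work. FEV₁ matters here because Protocol 4.3 justifies the 60 mg arm partly by the absence of lung-function improvement at lower doses so far. As planned, a dose-response statement on either endpoint would have to be read informally from pairwise differences and graphs.

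**Working it through.** **1. The two dose-response sections side by side**

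| | Primary endpoint (SAP 8.3.1.2) | ACQ-5 and FEV₁ (SAP 8.3.2.1.1) |
|---|---|---|
| Stated purpose | Increasing dose and effect | Increasing dose and effect |
| Test using dose order | Cochran-Armitage trend | None |
| Pairwise output | Odds ratios, dose against dose | All six pairs, Tukey-adjusted |

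SAP 8.3.2.1 adds each dose against placebo from the ANCOVA, and graphs. Neither tests dose order.

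**2. The plan's own power figure**

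The only stated power is for the primary endpoint (SAP 2.5): 25% against 10.2%, 80% power, two-sided 0.050, 8% dropout, 120 per arm.

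- Odds ratio = (0.102/0.898)/(0.25/0.75) = 0.341.
- n = (1.960 + 0.842)² × [1/(0.25 × 0.75) + 1/(0.102 × 0.898)] / (ln 0.341)² = 110.05 per arm.
- 110.05/0.92 = 119.6, so 120 per arm.

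The figure reproduces. It also gives the evaluable size used below: 120 × 0.92 = 110.4, taken as 110 per arm, with 4 × 110 − 4 = 436 degrees of freedom. No SD, effect size or power is given for ACQ-5, FEV₁ or any dose-response analysis, so the rest rests on assumed effects.

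**3. Critical values**

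Tukey, four arms, 436 df: q(0.95)/√2 = 3.647/√2 = 2.579, which is p < 0.0102 per pair. A single two-sided 0.05 test: 1.965.

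**4. Power of a linear contrast**

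With c = (-3, -1, 1, 3), Σc² = 20. Let m be the response shape with its largest value 1, and d the largest effect in SD units. Then δ = d × (c·m) × √(n/20), and power ≈ Φ(δ − 1.965). With n = 110, √(110/20) = 2.345. For d = 0.35 and a linear shape, c·m = 3.333, δ = 0.35 × 3.333 × 2.345 = 2.736, and power = Φ(0.771) = 78%.

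Tukey power (at least one of six pairs significant) comes from 400,000 simulated trials with the same n and df.

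| Shape: placebo, 20, 40, 60 mg | c·m | δ | Contrast | Tukey, any pair |
|---|---|---|---|---|
| Linear: 0, 1/3, 2/3, 1 | 3.333 | 2.736 | 78% | 60% |
| Emax-like, ED50 20 mg (assumed): 0, 0.67, 0.89, 1 | 3.222 | 2.645 | 75% | 65% |
| Plateau from 40 mg: 0, 0.5, 1, 1 | 3.500 | 2.873 | 82% | 70% |
| Flat from 20 mg: 0, 1, 1, 1 | 3.000 | 2.462 | 69% | 76% |
| Only at 60 mg: 0, 0, 0, 1 | 3.000 | 2.462 | 69% | 76% |
| Peak at 40 mg: 0, 0.5, 1, 0.5 | 2.000 | 1.642 | 37% | 57% |

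**5. Range of assumed effect**

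From d = 0.30 to d = 0.45:

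- Linear: contrast 65% to 94%, Tukey 46% to 84%.
- Flat from 20 mg: contrast 56% to 89%, Tukey 61% to 94%.
- Peak at 40 mg: contrast 29% to 56%, Tukey 43% to 81%.

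The direction of each comparison is the same across the range.

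**The case against.** Four points can be made for the plan.

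- **Tukey is not the efficacy test.** SAP 8.3.2.1 gives a difference, 95% CI and p-value for each dose against placebo, in general unadjusted. At 0.35 SD, 60 mg against placebo has δ = 0.35 × √(110/2) = 2.596 and power Φ(2.596 − 1.965) = 74%. The contrast's 78% under linearity is therefore only about 4 points better for detecting a drug effect. This stands. It limits what is lost, although those comparisons do not test dose order either.
- **A linear contrast is not always stronger.** A reader might infer that Tukey testing simply has less power than a trend test. The table contradicts that for three of six shapes. One of them, flat from 20 mg, is the pattern that SAP 2.5 assumes for the primary endpoint, with the same 10.2% in every GB001 group. Protocol 4.3 points the other way: it includes 20 mg as possibly suboptimal and 60 mg to look for more effect than 40 mg. The documents do not settle the shape.
- **A contrast that includes placebo does not isolate the active doses.** It reaches significance 69% of the time at 0.35 SD when 20, 40 and 60 mg are identical. This stands, and it is why the dose-against-dose estimates must stay. They address the question directly, though with little power: under a linear shape, at least one dose-against-dose pair is significant under Tukey in 17% of trials at 0.30 SD and 40% at 0.45 SD.
- **Descriptive information is already planned:** LS means by dose, bar graphs, box plots and simultaneous intervals. True, but none of it is a test or an estimate of trend.

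**Conclusion.** The concern holds in a narrow form. A section whose stated purpose is the relation between increasing dose and effect has no test that uses dose order and no trend estimate, while the parallel section for the primary endpoint has a trend test. That follows from the text and needs no power calculation.

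The power argument is conditional. At an assumed 0.35 SD and 110 per arm, the contrast gains 18 points if the response is linear (78 − 60), 10 if Emax-like (75 − 65) and 12 if it plateaus from 40 mg (82 − 70). It loses 7 points if the response is flat from 20 mg or present only at 60 mg (69 − 76), and 20 if it peaks at 40 mg (37 − 57).

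A reader might also set the contrast's 78% against the 51% that Tukey gives for 60 mg against placebo alone, since Φ(2.596 − 2.579) = 51%. That understates the plan, because Tukey tests all six pairs and the unadjusted comparison with placebo is reported separately.

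Severity is minor. These are secondary endpoints, the SAP sets no testing hierarchy among them, and no decision rule depends on the Tukey result.

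**What to change.** In SAP 8.3.2.1.1, for each of the two endpoints, prespecify a linear dose contrast with coefficients (-3, -1, 1, 3) for placebo, 20, 40 and 60 mg. Take it from the ANCOVA that is primary for that endpoint, with or without multiple imputation as SAP 8.3.2.1 determines. Report its estimate, 95% CI and p-value, two-sided at 0.050 in line with SAP 8.1.3. Because the doses are equally spaced, the contrast divided by 10 is the fitted change per 20 mg, which is easier to read.

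Keep the Tukey results and all pairwise differences as supportive. State that a significant contrast shows a trend across the four arms including placebo, and that any claim of a rise from 20 to 60 mg must rest on the dose-against-dose estimates and intervals.

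The cost is one contrast statement per model and one table row per endpoint, with no new data, visits or subjects. The price is lower power than Tukey for the flat, 60 mg-only and 40 mg-peak shapes, which keeping the pairwise output covers. The change belongs before the interim unblinding, because SAP Section 1 would label a later addition post hoc.

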8.3.2.2. Time to First Asthma Worsening

Time to first asthma worsening is defined as the time from the date of the first dose of study treatment to the first date that any of the components of the asthma worsening endpoint is met. Subjects who do not experience asthma worsening will be censored on the date of their last assessment for any of the components of asthma worsening. For the primary analysis of time to first asthma worsening, all data up to Week 24 will be utilized; a sensitivity analysis of time to first asthma worsening will be performed utilizing all data up to the Follow-up Visit (Week 28).

For subjects who experience asthma worsening, the date of the event is defined for each component as:

- AM PEF and rescue medication use date of event is considered to be on the first of 2 consecutive days where the respective criterion is met
- FEV₁ and ACQ-5 score date of event is considered to be on the date of the qualifying assessment
- Severe exacerbation date of event is considered to be on the date of onset of exacerbation as captured on the Severe Asthma Exacerbations eCRF

The number and proportion of subjects with asthma worsening will be summarized. The number and proportion of subjects meeting each component will also be summarized with subjects counted only once for the component first met.

Time to asthma worsening will be compared between treatment groups using a Cox proportional hazards model. The exact method will be used to handle ties in event times. Covariate adjustment will be the same as for the primary endpoint. Estimates of the hazard ratio for each GB001 group versus placebo, corresponding 95% CIs, and p-values will be provided from the model. Percentage reductions and corresponding 95% CIs will also be provided. Kaplan-Meier summaries of the proportion of subjects with asthma worsening over time will also be presented and displayed graphically. The median event time (and other quartiles), if estimable, and corresponding 95% CI based on the Brookmeyer and Crowley method (Brookmeyer, 1982) will be provided for each treatment arm.

Time to asthma worsening data will also be presented in a by-subject data listing.

8.3.2.3. Annualized Rate of Severe Asthma Exacerbations

A severe asthma exacerbation is defined as deterioration of asthma that leads to the use of systemic corticosteroids for at least 3 days, hospitalization, or an Emergency Department visit. Exacerbations for which the courses of systemic corticosteroids are separated by 7 or more days will be counted as separate severe asthma exacerbations.

The number and proportion of subjects with 0, 1, and ≥ 2 severe exacerbations and the annualized rate of severe asthma exacerbations will be summarized. The unadjusted annualized rate of severe exacerbations will be calculated as the total number of severe exacerbations divided by the total number of subject-years of follow-up and will also be summarized.

The total number of severe exacerbations will be analyzed using a negative binomial regression model, with the logarithmic transformation of follow-up time as the offset parameter. The follow-up time is defined as the subject's time on study up to and including Day 174. The model will include terms for treatment group, ICS dose (medium or high) at randomization, region, age at screening, and the number of exacerbations in the past 12 months. If the distribution of severe exacerbation data is under dispersed, or if the negative binomial regression model fails to converge, a Poisson regression model will be used instead of the negative binomial regression model. Exacerbations for which the courses of systemic corticosteroids are separated by 7 or more days will be counted as separate exacerbations.

Rate ratios for each GB001 group versus placebo, corresponding 95% CIs, and p-values will be provided from the model. In addition, the rate ratios and corresponding 95% CIs for the 3 pairwise comparisons among each of the GB001 treatment groups will be provided (60 mg vs 20 mg, 60 mg vs 40 mg, 40 mg vs 20 mg). Lastly, percentage reductions and corresponding 95% CIs will also be provided.

A sensitivity analysis will be performed to include asthma exacerbations that were treated with an intramuscular (IM) injection of systemic corticosteroids for less than 3 days. In this analysis, a severe asthma exacerbation will be defined as deterioration of asthma that leads to the use of oral or intravenous systemic corticosteroids for at least 3 days, the use of IM systemic corticosteroids for at least 1 day, hospitalization, or an Emergency Department visit.

Lastly, analyses of annualized rate of severe exacerbations will also be presented for the primary definition of severe asthma exacerbation by various time periods (Baseline to Week 12, Week 12 to Week 24, and Baseline through the Follow-up Visit [Week 28]) in order to elucidate onset and durability of effect over time.

This data will also be presented in a by-subject data listing.

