9.4.1.2. Secondary Efficacy Analysis

The secondary endpoints of change from baseline in ACQ-5 score, change from baseline in morning pre- and post- bronchodilator FEV₁, and change from baseline in morning PEF to Week 24 will be analyzed using analysis of covariance (ANCOVA) models. Differences in least-squares means, along with p-values and two-sided 95% CIs, for each GB001 group versus placebo will be constructed from the ANCOVA models.

Time to asthma worsening will be compared between treatment groups using a Cox proportional hazards model. Covariate adjustment will be the same as for the primary endpoint. Kaplan-Meier summaries of the proportion of subjects with asthma worsening over time will also be presented.

The annualized rate of severe asthma exacerbations will be analyzed using a negative binomial regression model, with the total number of severe exacerbations as the outcome and the logarithmic transformation of follow-up time as the offset parameter. Rate ratios, along with p-values and two-sided 95% CIs, for each GB001 group versus placebo will be constructed from the negative binomial regression model. If the distribution of severe exacerbation data is under-dispersed, or if the negative binomial regression model fails to converge, a Poisson regression model will be used instead of the negative binomial regression model. Exacerbations for which the courses of systemic corticosteroids are separated by 7 or more days will be counted as separate events.

[REDACTED]

[REDACTED]

[REDACTED]

[REDACTED]

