^a The analysis approach depends on the amount of missing data for the endpoint in the ITT population.

^b If the distribution of severe exacerbation data is underdispersed, or if the negative binomial regression model fails to converge, a Poisson regression model will be used instead.

^c Cross tabulations of the Baseline assessment versus the Week 24 assessment for Norwood classification (males) and Savin classification (females) separately.

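### The Poisson fallback for the severe exacerbation rate names no robust or scaled variance, so read naturally it assumes that the variance equals the mean

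*SAP*

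**What the plan says.** SAP 8.3.2.3 sets the main model: "The total number of severe exacerbations will be analyzed using a negative binomial regression model", with log follow-up time as the offset. Follow-up is "time on study up to and including Day 174". The covariates are treatment group, randomized ICS dose, "region, age at screening, and the number of exacerbations in the past 12 months".

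The fallback has two triggers: "If the distribution of severe exacerbation data is under dispersed, or if the negative binomial regression model fails to converge". In either case "a Poisson regression model will be used instead of the negative binomial regression model". On inference the section says: "Rate ratios for each GB001 group versus placebo, corresponding 95% CIs, and p-values will be provided from the model".

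Footnote b to SAP Table 1 ("If the distribution of severe exacerbation data is underdispersed, or if the negative binomial regression model fails to converge") and Protocol 9.4.1.2 ("If the distribution of severe exacerbation data is under-dispersed, or if the negative binomial regression model fails to converge") give the same two triggers and the same replacement model. So the three places agree on the model family. All three are silent on the standard error to be used with it, on the statistic or cut-off that defines under-dispersion, and on what is tried before non-convergence is declared. By comparison, SAP 8.3.1 sets out a stepwise covariate reduction for the logistic model, and SAP 8.3.2.1 gives alternative estimation and covariance choices for the MMRM.

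**The concern.** A Poisson model has no dispersion parameter. Unless a robust or scaled variance is requested, its standard errors are correct only if the variance equals the mean, given the covariates. Neither trigger establishes that.

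- **Under-dispersion.** If it is real, the variance is below the mean, so Poisson standard errors are too large and power is lost.
- **Non-convergence.** This is a numerical event and says nothing about dispersion. The fallback removes the parameter that was there to absorb over-dispersion. If over-dispersion is present, standard errors are too small.

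At stake are the intervals and p-values for a secondary endpoint that Protocol Amendment 2 raised from exploratory status. It is tested at a two-sided 0.050 without multiplicity adjustment (SAP 3 and 8.1.3). The rate is also analysed by time period (SAP 8.3.2.3) and in eosinophil and FeNO subgroups (SAP 8.4). Fewer events there make fitting trouble more plausible than in the main analysis.

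**Working it through.** **The plan's own figure.** The documents contain no design calculation for the exacerbation rate, and state no rate or dispersion. The only sample-size statement (SAP 2.5) concerns the primary binary endpoint. It reproduces with a Wald test on the log odds ratio: n = [1/(0.25×0.75) + 1/(0.102×0.898)] × (1.960 + 0.842)² / (ln 0.341)² ≈ 110.05 per arm, and 110.05/0.92 = 119.6, so 120. The present point does not touch it.

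**Inputs from the documents.** 120 per arm, four arms, 24 weeks, two-sided 0.050.

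**Assumptions, not in the documents.** Event rate 0.5, 1.0 or 1.5 per year (mean 0.23, 0.46 or 0.69 per 24 weeks). Over-dispersion is negative binomial with variance/mean φ = 1 + k × mean. Under-dispersion is Binomial(2, p) with φ = 1 − mean/2. No covariates and no dropout.

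**Formula.** If the true variance is φ times the Poisson variance, the Wald statistic has standard deviation √φ under the null, so size = 2[1 − Φ(1.96/√φ)]. The ratio of Poisson to true standard error is 1/√φ.

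**Results.** The simulated columns rest on 20,000 null trials per row.

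| Data | Rate/year | φ | Size, formula | Poisson SE, simulated | Sandwich SE, simulated |
|---|---|---|---|---|---|
| Under-dispersed | 0.5 | 0.885 | 0.037 | 0.034 | 0.047 |
| Under-dispersed | 1.0 | 0.77 | 0.026 | 0.026 | 0.049 |
| Under-dispersed | 1.5 | 0.655 | 0.015 | 0.015 | 0.051 |
| Poisson | 1.0 | 1.00 | 0.050 | 0.050 | 0.050 |
| k = 0.5 | 0.5 | 1.115 | 0.063 | 0.058 | 0.050 |
| k = 1 | 1.0 | 1.46 | 0.105 | 0.102 | 0.051 |
| k = 2 | 1.0 | 1.92 | 0.157 | 0.153 | 0.056 |
| k = 2 | 1.5 | 2.38 | 0.204 | 0.206 | 0.058 |

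A separate simulation that added k = 0.25 gave 0.014–0.034 for under-dispersed data and 0.051–0.193 for over-dispersed data with Poisson standard errors, and 0.047–0.056 with sandwich standard errors. The upper end for over-dispersion is therefore about 0.2. For interval width, φ = 0.77 gives 1/√0.77 = 1.14 (14% too wide) and φ = 1.46 gives 1/√1.46 = 0.83 (17% too narrow). Pearson scaling also worked, with sizes of 0.044–0.053.

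**What the under-dispersion trigger shows.** With truly Poisson data, sample dispersion fell below 1 in 52–53% of trials. In those trials the size with Poisson standard errors was 0.043–0.048, which is close to nominal.

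**How often the triggers meet over-dispersion.** With k = 0.5, sample dispersion fell below 1 in 0.01–8% of trials; with k of 1 or more, in under 1%. None of 2,400 unadjusted negative binomial fits (8 settings × 300) failed to converge.

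**The case against.** The strongest case against is that three tempting readings go beyond the documents.

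- **A reader might infer that the SAP prescribes model-based standard errors.** It does not. It says that results come from the model and leaves the estimator open. Ordinary Poisson inference is the natural reading, but it is a reading of silence.
- **A reader might infer that either trigger proves the Poisson variance wrong, so that intervals are wrong whenever the fallback is used.** That fails. No cut-off is given, and about half of truly Poisson trials show sample dispersion below 1, where plain Poisson is near nominal. Where under-dispersion is real, the error is conservative and adds no false positives.
- **A reader might take the inflated sizes as the expected effect.** They need a convergence failure together with real over-dispersion, which is the situation the negative binomial model is meant to fit. No such failure occurred in the fits above. Adjustment for prior exacerbations, age, region and ICS dose may also lower the residual dispersion.

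The remedy has a price too. In truly Poisson trials that look under-dispersed by chance, size was 0.047–0.048 with plain Poisson, 0.055–0.056 with sandwich and 0.054–0.055 with Pearson-scaled standard errors. Finally, the fallback is pre-specified consistently in three places, and the documents call this endpoint secondary, not key secondary.

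All of this stands, and it sets the severity. It does not close the gap: after a convergence failure nothing in the plan protects against over-dispersion. The absence of failures is limited evidence, because the fits were unadjusted and not run in SAS, and the sparse subgroups and time periods were not tested.

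**Conclusion.** The concern holds as a low-severity gap in specification. The fallback names no robust or scaled variance and so, read naturally, assumes that the variance equals the mean.

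- **Real under-dispersion:** intervals too wide, size about 0.014–0.034 (assumed φ 0.66–0.89).
- **Non-convergence with real over-dispersion:** intervals too narrow, size about 0.05–0.2 (assumed k 0.25–2, 0.5–1.5 events per year).
- **Data close to Poisson:** the planned inference is about right.

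These sizes are conditional on the dispersion assumed. How often the fallback would be used with the planned covariate model cannot be estimated from the documents, and in the main analysis it may never be used. The primary endpoint and the sample size are unaffected.

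**What to change.** In SAP 8.3.2.3 and in footnote b to SAP Table 1, state the fallback as Poisson regression with robust (sandwich) standard errors, and align Protocol 9.4.1.2. Pearson scaling would be an acceptable alternative, but one of the two should be named before unblinding. It would also help, though it is not essential, to state how under-dispersion is judged and what refitting is tried before non-convergence is declared.

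The cost is one phrase in each of three places and a standard software option, with no new data and no change in sample size. The statistical price is the slight excess over nominal size described above (about 0.055 instead of 0.048) when Poisson data look under-dispersed by chance. Against that, simulated size with sandwich standard errors stayed at 0.047–0.058 in every setting examined.

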Subjects will be provided with an eDiary which is programmed to alert the subject of potential asthma worsening:

1. On 2 consecutive days, AM PEF \leq 75% of mean AM PEF measured over the last 7 days of the Run-in period
2. Increase in rescue medication use of \geq 6 puffs/day (last 24 hours) on 2 consecutive days compared to mean use over the last 7 days of the Run-in period
3. Nighttime awakening due to asthma symptoms requiring rescue medication for at least 2 of 3 successive nights
4. An asthma symptom score of 4 for at least 2 of 3 successive days.

Upon receiving an alert, the subject should contact the site staff as soon as practical to assess the subject's asthma status. The subject may be asked to return to the clinic when necessary to have their asthma status evaluated.

Subjects who permanently discontinue IP will be requested to attend the Early Discontinuation of IP visit and will be strongly encouraged to complete any remaining study visits as per the Schedule of Activities (SoA; [Section 1.3](#)). Subjects who permanently discontinue IP and continue in the study will complete the Early Discontinuation of IP visit at the time of IP discontinuation and then return for the next visit in the Double-Blind, Placebo-Controlled visit sequence. At the visits subsequent to the Early Discontinuation of IP visit, study procedures will be completed except for dispensation/return of IP. Subjects who withdraw from the study, regardless of the reason, will be requested to return to the clinic to complete the Early Withdrawal (EW) from Study visit. All subjects who remain on IP through and including Visit 9 (Week 24) or who complete the EW from Study visit will be asked to return for a Follow-up visit approximately 4 weeks after their last dose of IP to assess subject safety.

Total duration for study participation per subject is up to 34 weeks (includes a Screening visit, followed by a 2-week to 6-week Run-in period to allow for collection of baseline eDiary data; a 24-week Double-Blind, Placebo-Controlled period; and 4-week Follow-up period).

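### The by-period severe-exacerbation analyses aim at onset and durability, but none estimates whether the effect changes between periods or isolates the weeks after stopping drug

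*SAP*

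**What the plan says.** The last analysis in SAP 8.3.2.3 presents the severe-exacerbation rate in three windows and gives the purpose: "Baseline to Week 12, Week 12 to Week 24, and Baseline through the Follow-up Visit [Week 28]) in order to elucidate onset and durability of" the drug's benefit.

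No separate model is given for these periods. The one model in the section is stated as follows: "The total number of severe exacerbations will be analyzed using a negative binomial regression model", with log follow-up time as offset. On covariates: "The model will include terms for treatment group, ICS dose (medium or high) at randomization, region, age at screening, and the number of exacerbations" over the previous year. There is no period term and no treatment-by-period term. On output: "Rate ratios for each GB001 group versus placebo, corresponding 95% CIs, and p-values will be provided from the model". Follow-up time for the offset is the subject's "time on study up to and including Day 174", and it is not restated for the shorter or longer windows. Protocol 9.4.1.2 adds no between-period contrast.

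On the end of the third window, Protocol 4.1.1 says that subjects who stay on drug through Week 24 "will be asked to return for a Follow-up visit approximately 4 weeks after their last dose of IP to assess subject safety". The schedule of activities dispenses no study drug at Week 24. Under Protocol 7.1, a subject who stops drug before Week 20 and stays to Week 24 need not attend the follow-up visit.

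**The concern.** Whether an effect emerges late or wanes is a question about change in the rate ratio over time. As written, the plan gives a drug-versus-placebo rate ratio in each window and no estimate of the difference between windows. The two 12-week windows hold the same subjects, so their two confidence intervals do not supply the standard error of the change.

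The third window contains the other two. The three therefore cannot be levels of one period factor, and separate fits are the only workable reading. Weeks 24 to 28, the only time that completers are off drug, are never shown alone.

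The SAP uses the right tool elsewhere: a treatment-by-subgroup interaction in 8.4, and a treatment-by-visit term in the repeated-measures model of 8.3.2.1. The analysis whose stated purpose is the time course has no such term. At stake is the wording of the report: a steady effect could be described as delayed or waning because one half-study comparison reached significance and the other did not.

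**Working it through.** **The plan's own figure.** The SAP gives no power or precision for the by-period analyses. Its one figure, 80% for the primary endpoint (SAP 2.5), reproduces. OR = (0.102/0.898)/(0.25/0.75) = 0.341; n = 120 × 0.92 ≈ 110 per arm; SE of log OR = √[1/(110×0.25×0.75) + 1/(110×0.102×0.898)] = 0.384; power = Φ(1.077/0.384 − 1.96) ≈ 80%. It does not bear on exacerbation rates.

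**Inputs.** From the documents: 120 per arm, two-sided 0.05 without multiplicity adjustment (SAP 8.1.3), and windows of 12, 12 and 4 weeks. Assumed, because the documents do not give them: placebo rate 0.5, 1.0 or 1.5 per year; negative binomial dispersion 0.5 to 1; a constant rate ratio (RR) of 0.5 or 0.7; no dropout; one dose against placebo.

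**Constant effect.** Expected placebo events per 12-week window are 120 × 84/365.25 × rate = 13.8, 27.6 and 41.4. Simulated counts shared a subject-level frailty across windows. Each window had a negative binomial Wald test, counted as significant when in favour of drug. The change was tested by the log ratio of the two rate ratios. Exactly one significant = P(first) + P(second) − 2 × P(both). Results at RR 0.5 throughout, dispersion 1, 6,000 trials per row:

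| Placebo rate/yr | Weeks 0–12 sig. | Weeks 12–24 sig. | Both | Exactly one | Early only | Treatment-by-period sig. |
|---|---|---|---|---|---|---|
| 0.5 | 27.7% | 27.4% | 8.3% | 38.6% | 19.5% | 3.9% |
| 1.0 | 50.3% | 50.4% | 27.6% | 45.5% | 22.7% | 4.1% |
| 1.5 | 64.7% | 65.0% | 45.4% | 39.0% | 19.4% | 4.3% |

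Check for the middle row: 50.3 + 50.4 − 2 × 27.6 = 45.5. Across dispersion 0.5 to 1, the exactly-one figure runs from about 37% to 47%, and the treatment-by-period figure from about 4% to 6%. At a constant RR of 0.7, the exactly-one figure is about 19% to 37%.

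**Precision of the direct contrast.** The SE of the log ratio of rate ratios is about √(Σ 1/events) over the four arm-by-window cells. At rate 1.0 and RR 0.5: √(2/27.6 + 2/13.8) = 0.466, so the 95% CI is ×/÷ exp(1.96 × 0.466) ≈ 2.5. Simulated factors are 3.70, 2.51 and 2.12 at rates 0.5, 1.0 and 1.5. If an RR of 0.5 is lost after Week 12, the contrast's power at dispersion 1 is 19%, 35% and 50%; other runs over dispersion 0.5 to 1 gave about 20% to 52%.

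**The Week 28 window.** The off-drug share is 4/28 = 14.3%. With RR 0.5 on drug and a flat placebo rate, the expected cumulative ratio is 0.50 if the effect persists after stopping, and (24 × 0.5 + 4 × 1)/28 = 0.57 if it ends at once. The window barely separates the two cases. With RR 0.4 on drug (rate 1.0, dispersion 1) and none after, it is still significant in 83% of trials. That is a correct rejection of no effect, but it carries almost no information about Weeks 24 to 28. Expected placebo events in those weeks alone are 120 × 28/365.25 × rate = 4.6 to 13.8.

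**The offset.** By the target-day rule in SAP 3.1, Week 12 is Day 85 (12 × 7 + 1) and Week 28 is Day 197 (28 × 7 + 1). A cut-off at Day 174 fits neither.

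**The case against.** The strongest defence is that the windows do address durability in a reasonable sense. The Week 12 to 24 rate ratio, with its CI, estimates whether an effect is present in the second half. That stands. A reader might infer that the planned tables say nothing about whether the effect lasts; the documents do not support that.

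Nor do they support the fear that an effect confined to Weeks 0 to 12 would pass as durable on the Week 28 result. With RR 0.3 and then 1, the Week 28 window was significant in about 20% to 50% of trials. The Week 12 to 24 table sits beside it, however, and both were significant in only about 2% to 3%.

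The SAP also sets no significance rule for these tables. That p-values will appear per window is an inference from the main model's output. Durability is not defined as persistence after stopping, and extension to Week 28 recurs in SAP 8.3.1.3 and 8.3.2.2. All this is fair. It limits the harm but does not supply the missing estimate of change.

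Finally, the direct contrast is imprecise and would often be inconclusive. That is a reason to report it as an estimate with a CI; it does not make two separate comparisons a substitute.

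**Conclusion.** The concern holds as a minor point. The stated aim is onset and durability, yet no planned analysis estimates the change in effect between the two halves of treatment, and none isolates the weeks after stopping.

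The 37% to 47% discordance (19% to 37% at RR 0.7) rests wholly on the assumed rates, dispersion and rate ratios. A reader might take it for a false-positive rate; it is not. It is what low power in two half-length windows produces when a real effect is constant. It misleads only if onset or durability is read from which window has p < 0.05. Likewise, a significant Week 28 result after an on-drug effect is not an error; it simply answers a different question.

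The documents call this endpoint secondary, with no higher rank. The primary endpoint and the main Week 24 rate ratio are unaffected.

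**What to change.** Keep the Baseline to Week 12 and Week 12 to 24 rate ratios, but obtain them from one model on subject-period counts:

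- Use disjoint periods (Weeks 0–12, 12–24 and 24–28), log time in period as offset, the same covariates, treatment, period and treatment-by-period, with a subject-clustered variance.
- Report the ratio of rate ratios (Week 12–24 over Baseline–Week 12) with its 95% CI, as estimation. Report Weeks 24–28 as an estimate with CI only.
- Label any Baseline to Week 28 table as *on- plus off-treatment*.
- State that onset and durability statements rest on the period estimates and their ratio, not on which periods reach p < 0.05, and that a non-significant interaction is not evidence of durability.

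The cost is SAP wording and one model on data already collected. The downside is visible imprecision: under the assumed rates the 95% CI on the ratio is about ×/÷ 2.1 to 3.7, power is about 20% to 52% if an RR of 0.5 is lost after Week 12, and Weeks 24–28 would hold only about 5 to 14 placebo events.
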